## 4.8. Population Pharmacokinetic (PopPK) Analyses

The primary goal of this analysis is to characterize the population pharmacokinetics of mepolizumab administered subcutaneously in participants with CRSwNP / ECRS. The analysis will be based on the most recent population pharmacokinetics model established with historical data from various indications. The influence of demographics, baseline characteristics, including disease activity, and co-medication on the pharmacokinetics of mepolizumab in this population will also be investigated. These data will be used to explore potential ethnic differences between Japanese/Chinese and Caucasians in mepolizumab exposure. The individual participant PK parameters will be estimated and documented for the purposes of any subsequent exposure-response (PK/PD) analyses.

Mepolizumab plasma concentration-time data [samples collected at Weeks 4, 28 and 52; at the Early Withdrawal Visit and additional visits (if applicable)] will be analysed by population methods using nonlinear mixed-effects modelling. The analysis will be carried out using appropriate software (e.g. NONMEM™ or SAS™).

In support of the analysis described below, a dataset will be generated for which specifications will be provided in a separate document.

### 4.8.2. Main Analytical Approach

A population PK analysis of sparse concentration data will be performed. The population of interest will be the entire trial population (patients meeting the study inclusion/exclusion criteria with a diagnosis of CRSwNP / ECRS) who are randomised and receiving study treatment with at least 1 non-missing PK assessment (PK analysis set).

The summary measure of interest will be the log-transformed mepolizumab plasma concentration. For participants prematurely discontinuing study treatment, all available data will be included in the analysis (intercurrent event to be handled using a treatment policy strategy).

Sparse blood sampling is implemented in this study for determination of mepolizumab plasma concentration and subsequent data analysis by population PK methods using the

most recent population pharmacokinetics model (meta-analysis PK model of data across indications described in GSK Document Numbers: [2015N238436\\_00](#) and [2020N427698\\_00](#)). The main objectives of this population PK analysis are:

- To evaluate mepolizumab pharmacokinetics in participants with CRSwNP / ECRS following the subcutaneous administration of a 100 mg dose every 4 weeks;
- To investigate the impact of covariates of interest in the studied CRSwNP / ECRS population (such as baseline characteristics, co-medication) on specific parameters (e.g. clearance) to identify potential sources of inter-individual variability in these parameters;
- To obtain individual plasma concentration predictions for the timepoints at which PD is measured to allow the conduct of population PKPD analyses if deemed appropriate.

Outlier data will be assessed for plausibility; however, the aim is to use all available data whenever possible. Any decision to exclude data will be fully documented and specified in the clinical study report.

Further details of the Population PK analyses will be provided in the Output and Programming Specification (OPS) document.

#### 4.8.3. Supplementary Analyses

Complementing the population-PK analysis, an additional analysis of a repeated measures linear mixed-effects model of log-transformed concentration will be used to analyse the sparse PK data. All data will be analysed on an Intent-to-Treat basis using planned Visit, irrespective of discontinuation of study treatment (to be handled using a treatment policy strategy).

The model will adjust for covariates of country, log bodyweight, log creatinine clearance, log serum albumin with a repeated term for Visit. An unstructured covariance structure for the R matrix will be used by specifying ‘type=UN’ on the REPEATED line. The Kenward and Roger method for approximating the denominator degrees of freedom and correcting for bias in the estimated variance-covariance of the fixed effects will be used. Selection of covariates will be based on biological plausibility, parsimony and a significance level of 0.05. Forwards and backwards selection criteria may be applied as per the population PK model.

The estimated means for each visit will be calculated from the model using the observed marginal distributions of the sample covariates (OM option in LSMEANS statement). Model-estimates of the absolute mean and mean ratio to Week 4 (accumulation ratio) will be back-transformed and presented as ratios with corresponding standard errors on the log scale by visit. Estimated exposure ratios with corresponding 95% CIs and p-values will also be presented. The effects of bodyweight, creatinine clearance and serum albumin will be evaluated as a ratio to standard values and back transformed and presented as ratios with corresponding standard errors on the log scale. Estimated exposure ratios with corresponding 95% CIs and p-values will also be presented.

## 4.9. Population Pharmacokinetic/Pharmacodynamic (PopPKPD) Analyses

If deemed appropriate, a population pharmacokinetic/pharmacodynamic analysis will be conducted. Mepolizumab blood eosinophil count-time data will be analysed by population methods using nonlinear mixed-effects modelling. The analysis will be carried out using appropriate software (e.g. NONMEM or SAS).

In support of the analysis described below, a specific dataset will be generated for which specifications will be provided in a separate document.

### 4.9.1. Definition of Endpoint(s)

Blood for PK are defined within Section 4.8.1.

Blood eosinophil counts are defined within Section 4.7.1.

### 4.9.2. Main Analytical Approach

The population of interest will be the PK analysis set and the ITT analysis set (for blood eosinophils). For participants prematurely discontinuing study treatment, all available data will be included in the analysis (intercurrent event to be handled using a treatment policy strategy).

This PopPKPD analysis will be performed by population methods using the most recent population PKPD model [meta-analysis PKPD model of data across indications described in GSK Document Numbers: [2020N427698\\_00](#), [2015N238436\\_00](#) and [2015N255079\\_00](#) (extension of the former report)].

The objectives of the popPKPD analysis are:

- To evaluate mepolizumab pharmacodynamics in participants with CRSwNP / ECRS following subcutaneous administration of a 100 mg dose every 4 weeks;
- To investigate the impact of covariates of interest in the studied CRSwNP / ECRS population (such as baseline characteristics, co-medication) on specific parameters (e.g. maximum blood eosinophil reduction) in order to identify potential sources of inter-individual variability in these parameters.

[figure not shown]
Outlier data will be assessed for plausibility; however, the aim is to use all available data whenever possible. Any decision to exclude data will be fully documented and specified in the clinical study report.

Further details of the popPKPD analyses will be provided in the Output and Programming Specification (OPS) document.

[figure not shown]
## 4.10. Genetics Analysis

A separate analysis plan will be produced for any analysis of genetic data.

[figure not shown]
CCI

CCI

CCI

## **4.12. Interim Analyses**

No interim analysis of data is planned for this study.

#### 4.13. Changes to Protocol Defined Analyses

The changes from the originally planned statistical analysis specified in the Protocol Amendment 3 [GlaxoSmithKline Document Number: [TMF-14790303](#). Dated: 21-Jul-2022] are described in [Table 3](#).

**Table 3 Changes to Protocol Defined Analyses**

Protocol Defined Analysis	SAP Defined Analysis	Rationale for Changes
Time to first 'need for surgery' (NP score $\geq 5$ and overall VAS symptom score $>7$ ) up to Weeks 4, 8, 24 and 52	Need for surgery (NP score $\geq 5$ and overall VAS symptom score $>7$ ) at Week 52	It is expected that patients will enter the study with a 'need for surgery' due to requirement to meet inclusion criteria of severe NP symptoms.
Lund Mackay CT score at Week 52 will use the same population, summary measure and strategies for intercurrent events as for the primary estimands. Analysis methods will be the same as for the co-primary endpoints.	Lund Mackay CT score at Week 52 will use the same population, summary measure and strategies for intercurrent events as for the primary estimands. Analysis methods will be based on ANCOVA.	Lund Mackay CT score is recorded once post-baseline at Week 52, therefore assessment of change from baseline via ANCOVA analysis is appropriate.

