3. Parasitic screening is only required in countries with high-risk or for participants who have visited high-risk countries in the past 6 months. Sites should use local laboratories
4. A CT scan should be performed anytime during the run-in period up to a week prior randomisation. A second CT scan should be performed at V15 or IP discontinuation/Early Withdrawal visit (up to 14 days prior to the nominal study visit)
5. Urine Pregnancy test results to be assessed at all visits and prior to CT scan at Screening, V15 or IP discontinuation/Early Withdrawal Visit. If a urine test cannot be confirmed as negative (e.g., an ambiguous result), a serum pregnancy test is required.
6. eDiary completion by participants will be daily every morning between Screening Visit and Visit 15 (or IP discontinuation/Early Withdrawal Visit)
7. Genetics informed consent to be obtained any time prior sampling, Genetics sampling to be performed anytime while on treatment (Genetics sampling not applicable for participants in China)
8. Performed using eDiary device
9. All questionnaires will be performed before any other assessments on each particular visit, VAS scores (if not already completed at home), SNOT-22, (ACQ-5), SF-36 and WPAI. ACQ-5 should only be performed in Asthmatic participants. Order of questionnaires will be detailed in the Study Reference Manual.
10. SF-36 and WPAI will be performed at visits Baseline, week 4, week 24 and week 52 (or IP discontinuation/Early Withdrawal Visit) only
11. For endoscopic NP scores performed at V1, 3, 4, 6, 8, 10, 12, 14, 15 (or IP discontinuation/Early Withdrawal Visit), the nasal endoscopy assessment may be performed up to 3 days prior to the day of dosing but must not exceed the protocol defined windows of ±7 days from the nominal study visit. For V2, the endoscopic NP score cannot be performed earlier than V2 but must be performed at V2 upon completion of all screening procedures and prior to administration of IP.

12. For asthmatic participants only. An asthma exacerbation is defined as worsening of asthma requiring systemic corticosteroids (i.v. or oral steroid) for at least 3 days or a single IM CS dose and/or emergency department visit, or hospitalisation

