Potential risk of immunogenicity	
Mepolizumab has low immunogenic potential. Overall, the immunogenicity results from clinical studies across the mepolizumab program demonstrate that the presence of anti-drug antibodies (ADAs) is not associated with any specific adverse events, anti-mepolizumab antibodies did not discernibly impact the pharmacokinetics (PK) or pharmacodynamics (PD) of mepolizumab in the majority of participants and there was no evidence of a correlation between antibody titres and change in eosinophil level.
 
Immunogenicity data reported to date across the mepolizumab development program are summarized in the IB; See Section 5.4 'Clinical Immunogenicity' and in Section 6 'Summary of Data and guidance for the Investigator' [GSK Document Number CM2003/00010/10, 2015].
	Blood samples will be collected for detection of both ADA and neutralising antibodies (NAb).
Study Procedures		
Potential risk for injury with phlebotomy	Risks with phlebotomy include bruising, bleeding, infection, nerve damage.	Procedures to be performed by trained personnel (i.e., study nurse)
Exposure of subjects to ionising radiation from Cranial CT	
Two cranial CT scans are included at visits 1 and 15, or in the event of IP discontinuation / Early Withdrawal.
 
The total effective radiation dose from the two cranial CT procedures is estimated to be 4mSv.
 
The average annual global background radiation dose is 2.4mSv and therefore the total estimated
	The minimum number of CT procedures will be performed to achieve study objectives (with a 52 weeks spacing between procedures). Application of an increased minimum age for inclusion in the study was considered to further mitigate the risks. However, such a restriction is impracticable in this population and might also result in the study sample being skewed and unrepresentative. Therefore,

Important Identified Risk	Summary of Data/Rationale for Risk	Mitigation Strategy
	dose from study procedures is less than 2-years of background radiation. The additional risk of developing a fatal malignancy as a result of this radiation exposure is around 1 in 5000.	given the moderate radiation dose, a minimum age for inclusion of 18 years is considered justifiable.

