8.1.5. Critical procedures performed throughout treatment period

8.1.5.1. Daily eDiary

All to be performed daily at home, including at study visit days.

- Overall VAS symptom score
- VAS for nasal obstruction, nasal discharge, mucus in the throat, loss of smell, facial pain

8.1.5.2. (Visits 2 - 15)

- eDiary at site
 - SNOT-22 questionnaire (selected visits only)
 - ACQ-5 (for asthmatics) (selected visits only)
 - SF-36 (selected visits only)
 - WPAI-GH (selected visits only)
 - Review eDiary and retrain if required
- Assessment of nasal surgery (confirmed and waiting list)
- Assessment of systemic CS dose and duration
- Endoscopic NP score (be performed at selected visits only, refer to SoA)
- End of study cranial CT scan (V15 or IP discontinuation/Early Withdrawal Visit, – performed within the visit window and up to 14 days before study visit)
- Blood for PK (to be done only at visits and in countries indicated in the SoA)
- Genetic sample (to be done one time only in any of the visits for non-Chinese participants) as per SoA
- AE/SAE review
- Concomitant medication review
- 12-lead ECG as per SoA

- Vital signs as per SoA
- Laboratory assessments as per SoA
- Blood for immunogenicity as per SoA
- Urinalysis as per SoA
- Urine pregnancy test (for all WOCBP) as per SoA
- FSH and oestradiol will be assessed to confirm child-bearing status (following a positive urine test)

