8.2.2. Computed Tomography (CT) Scan

The Lund Mackay (LMK) CT scoring system is based on localization with points given for degree of opacification: 0 = ~~CCI~~ [REDACTED], 1 = ~~CCI~~ [REDACTED], 2 = ~~CCI~~ [REDACTED]. These points are then applied to the maxillary, anterior ethmoid, posterior ethmoid, sphenoid, frontal sinus on each side. The osteomeatal complex (OC) is graded as 0 = ~~CCI~~ [REDACTED] or 2 = ~~CCI~~ [REDACTED]. This scoring system has been validated in several studies.

For patients in whom the OC is missing (because of a previous surgery) the reader should consider the location of the former OC and provide a scoring (as if the OC was there).

CT scan should be performed anytime during the run-in, and at Visit 15 (Week 52) and IP discontinuation/Early Withdrawal Visit.

Details for CT will be available in a separate operational manual provided to the sites. CT scans central reading for LMK scoring will be used in the statistical analysis [Appendix 10](#).

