8.3.5. Pregnancy Testing

- Refer to Section [5.1](#) Inclusion Criteria for pregnancy testing entry criteria.
- Pregnancy testing should be conducted at monthly intervals during the study intervention period, preferably as part of the regular onsite study visits. If a urine test cannot be confirmed as negative (e.g., an ambiguous result), a serum pregnancy test is required.
- Pregnancy testing must be conducted for each WOCBP prior to the cranial CT scan assessment which will be performed anytime during the run-in, and at Visit 15 (Week 52) and the IP discontinuation/Early Withdrawal Visit.
- Pregnancy testing should be conducted at the end of relevant systemic exposure plus an additional 30 days and correspond with the time frame for female participant contraception in Section [5.1](#) Inclusion Criteria (contraception to be taken during the study intervention period and for at least 105 days after the last dose of study intervention).
- Additional pregnancy tests may be performed, as determined necessary by the investigator or required by local regulation, to establish the absence of pregnancy at any time during the participant's participation in the study.

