#### 4.3.1.3. Lund Mackay CT Score

The Lund Mackay CT scoring system is based on localization with points given for degree of opacification: 0 = **CCI** [REDACTED], 1 = **CCI** [REDACTED], 2 = **CCI** [REDACTED]. These points are then applied to the maxillary, anterior ethmoid, posterior ethmoid, sphenoid, frontal sinus on each side. The osteomeatal complex (OC) is graded as 0 = **CCI** [REDACTED], or 2 = **CCI** [REDACTED]. This scoring system has been validated in several studies [Bhattacharyya, 1999; Lund, 1993]. For patients in whom the OC is missing (because of a previous surgery) the reader should consider the location of the former OC and provide a scoring (as if the OC was there).

A CT scan should be performed anytime during the run-in, and at Week 52 and IP discontinuation/Early Withdrawal Visit. CT scans central reading for Lund Mackay CT score will be used in the statistical analysis. The primary assessment will be at Week 52. Baseline will be defined as the latest non-missing measurement collected prior to the first dose of study treatment (Section 4.1.2.1).

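### Lund-Mackay CT (H4): the documents conflict on whether a participant who stops IP but stays in follow-up has a Week 52 scan

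*SAP*

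**What the plan says.** SAP Table 3 replaces the repeated-measures model with ANCOVA for Lund-Mackay CT because "Lund Mackay CT score is recorded once post-baseline at Week 52, therefore assessment of change from baseline via ANCOVA analysis is appropriate".

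The second scan is described in two ways.

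- **Or.** Protocol 1.3, SoA footnote 4: "A second CT scan should be performed at V15 or IP discontinuation/Early Withdrawal visit". Protocol 2.3.1: "Two cranial CT scans are included at visits 1 and 15, or in the event of IP discontinuation / Early Withdrawal", with a total of 4 mSv and the mitigation "The minimum number of CT procedures will be performed to achieve study objectives (with a 52 weeks spacing between procedures". Protocol 8.1.5.2: "End of study cranial CT scan (V15 or IP discontinuation/Early Withdrawal Visit".
- **And.** Protocol 8.2.2: "and at Visit 15 (Week 52) and IP discontinuation/Early Withdrawal Visit". Protocol 8.3.5, on pregnancy tests before CT: "and at Visit 15 (Week 52) and the IP discontinuation/Early Withdrawal Visit". SAP 4.3.1.3: "A CT scan should be performed anytime during the run-in, and at Week 52 and IP discontinuation/Early Withdrawal Visit".

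The SoA grid marks CT under both V15 and the IP discontinuation/Early Withdrawal column. Protocol 7.1.4 lists a CT at the IP Discontinuation Visit, 4 weeks after the last dose. Protocol 7, 7.1.1 and 7.1.4 ask that participants who stop IP be followed to Week 52 where possible.

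SAP 1.1.2 and Table 3 give H4 the same intercurrent-event strategies as the co-primaries. SAP 4.2.2 therefore applies: IP discontinuation unrelated to COVID-19 is treatment policy, and off-treatment data are included. Missing data are assumed missing at random, a rule that H4 takes over through SAP 4.3.2.

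**The concern.** A site cannot tell from the text whether to scan a retained discontinuer at Week 52. If it follows *or* and the two-scan count, the value that the H4 estimand asks for is missing by design, in someone who is still attending. No analysis convention, including any in the Output and Programming Specification, can supply a scan that was not taken.

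The ANCOVA uses one post-baseline value, so it leaves such a participant out. Unlike the co-primary MMRM, it has no intermediate visits of the same endpoint to draw on. The off-treatment imputation in SAP 4.2.3 is written for the co-primaries, and the visible text gives no equivalent for H4.

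H4 is one of the two secondaries tested first, at 0.025. It is retested at 0.05 only if H3, H5, H6 and H7 are all rejected. SAP 2.1 calls it important in clinical practice in Japan and China, the countries where registration is sought.

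**Working it through.** **Each wording applied to a retained discontinuer**

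| | *Or*, two scans in total | *And* |
|---|---|---|
| Post-baseline scans | one, early | two |
| Week 52 CT | no | yes |
| Two-scan count in 2.3.1 | met | exceeded |
| 52-week spacing in 2.3.1 | not met | not met for the early scan |
| Table 3 premise (once, at Week 52) | once, but not at Week 52 | at Week 52, but not once |

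Neither wording satisfies everything the documents say, and the Table 3 premise fits this participant under neither.

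**Timing of the early scan.** Stopping IP means no dose at Week 48 (Protocol 7.1.4), so the last dose is between Week 0 and Week 44. Adding 4 weeks gives a nominal Week 4 to Week 48. The visit is 28 ± 7 days after the last dose, and the CT may precede the nominal visit by up to 14 days, so the scan falls at about day 28 − 14 = 14 to 28 + 7 = 35. SAP 4.2.3 defines off-treatment as over 28 days after the last dose, so most of these scans would count as on-treatment.

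**Dose.** Two scans at 4 mSv are 4/2 = 2 mSv each, and 4/2.4 = 1.7 years of background, which agrees with the statement in 2.3.1 of less than 2 years. Three scans would be 6 mSv, or 6/2.4 = 2.5 years.

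**Size.** The documents give no power, effect, SD or discontinuation rate for H4, so there is no planned H4 figure to reproduce. The co-primary power does reproduce (noncentral t, 80 per arm: 93.24% and 97.18% against the stated 93.2% and 97.2%). What follows is illustration on assumed inputs.

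Let *d* be the share per arm of retained discontinuers without a Week 52 CT (assumed 5–15%), *D* the effect in scanned participants, and *f* the share of the effect that mepolizumab discontinuers keep.

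- Counts: 80 × 0.05 = 4; 80 × 0.15 = 12 per arm.
- The treatment-policy effect is *D*(1 − *d*(1 − *f*)) and the observed-case estimate is *D*, so the ratio is 1/(1 − *d*(1 − *f*)).
  - *f* = 1: 1.000, no bias.
  - *f* = 0.5: 1/0.975 = 1.026 to 1/0.925 = 1.081.
  - *f* = 0: 1/0.95 = 1.053 to 1/0.85 = 1.176.
- Opposite case, with placebo discontinuers worse by an amount equal to *D*: the ratio is 1/(1 + *d*) = 0.952 to 0.870.
- Standard error factor 1/√(1 − *d*): 1.026 to 1.085.
- Power at an assumed 0.5 SD and alpha 0.025: 81.5% with 80 per arm, 79.2% with 76, 74.1% with 68.

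**The case against.** The strongest reply is that *or* need not be exclusive. SoA footnotes 10, 11, 15 and 16 attach the same phrase to SF-36, WPAI, endoscopy and laboratory tests. Read exclusively, footnote 11 would end endoscopy, a co-primary assessment, at the IP discontinuation visit, which contradicts Protocol 7. The phrase may therefore be list style. The grid marks CT in both columns, and 7.1.1 and 7.1.4 follow discontinuers through the Week 52 assessments, of which CT is one. Protocol 8 requires adherence to the SoA but does not rank it above 8.2.2. The 52-week spacing also speaks against an early-only scan.

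This stands as far as it goes: a reader might infer that the plan definitely leaves retained discontinuers without a Week 52 CT, and the documents do not establish that. But CT differs from the other assessments in two respects: footnote 4 speaks of a second scan, and 2.3.1 counts two. The *and* sentences can equally be read as a list of possible time points. The conflict remains.

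The numbers are also open to fair objection. The 5–15% is not from the documents and is not reduced for three groups whose result would not change: surgery cases, who receive the worst possible score; COVID-19-related discontinuers, whose later data are excluded; and participants followed by telephone only, who have no Week 52 CT under any wording.

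**Conclusion.** The conflict is in the current text and should be resolved; the weight is minor to moderate. On the *or* reading with two scans, the Week 52 value needed for H4 is missing by design in retained discontinuers and the ANCOVA omits them. On the *and* reading, the stated scan count and dose are exceeded.

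Three stronger inferences are not supported. ANCOVA is not an error: one analysis visit is a sound reason for it, and only the wording of the Table 3 rationale is inaccurate. H4 is not without a missing-data rule, since missing at random is inherited from SAP 4.2.2. Nor can H4 be said to favour mepolizumab: on the assumed inputs the estimate runs from 13.0% too small to 17.6% too large, and is unbiased if the unscanned resemble comparable scanned participants. The 17.6% needs the exclusive reading, 15% retained discontinuers and complete loss of effect together.

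**What to change.** 1. Use one wording in Protocol 1.3 (footnote 4 and the CT row of the grid), 2.3.1, 7.1.4, 8.1.5.2, 8.2.2 and 8.3.5, and in SAP 4.3.1.3: *The second CT is done at Week 52 in every participant still in follow-up, including those who have stopped IP. It is done early only in a participant who is leaving the study.* Anyone already scanned early is not rescanned.
2. State in the SAP that an early CT is not used as the Week 52 value.
3. Reword the Table 3 rationale: *Lund-Mackay CT has one analysis visit after baseline (Week 52).* Keep ANCOVA as the H4 analysis.
4. Optional: a multiple-imputation sensitivity analysis for H4. It would assign 24, the maximum score, to surgery cases, impute missing Week 52 CT from baseline CT, the model covariates, endoscopic score history and, where the data allow, on/off-treatment status, and pool with Rubin's rules.

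The cost is clarified wording in two documents. There is no added planned scan, visit or participant, and exposure stays at two scans and 4 mSv. The downside is that a discontinuer who later withdraws may have no second CT, because Protocol 7.2.2 waives the early withdrawal visit once an IP discontinuation visit has taken place.
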